6.3 Efficacy

Unless otherwise noted, the primary and secondary efficacy analyses will be conducted on the mITT population. All efficacy data will be included in listings by subject, treatment group, and visit (as applicable). When applicable, the efficacy analyses will be presented for the double-blind and OLE phases, separately and combined. For the OLE phase, no inferential statistics will be derived.

For the double-blind phase, baseline is considered as the last available assessment on or before the first day of study treatment. For the OLE Phase, baseline is considered as (1) the double-blind Week 48 visit assessment for subjects who have been off of the study drug for less than or equal to 4 weeks, or (2) the OLE Baseline-Extension visit assessment for subjects who have been off of the study drug for greater than 4 weeks.

Table 4: Primary, Secondary, and COL Efficacy Estimands and Analyses

Index	Description	Variable Type	Treatment Group Comparison	On-Study Data
Prima	ry Estimand			
P01	Difference between treatment groups in change from baseline in the modified UMSARS scores at Week 48 of the DB Phase	Continuous	MMRM	Screening, Baseline, Weeks 4, 12, 24, 36, 48,
Second	lary Estimand			
S01	Difference between treatment groups in change from baseline in CGI-I score at Week 48 of the DB Phase	Continuous	MMRM	Weeks 4, 12, 24, 36, 48
S02	Difference between treatment groups in change from baseline in MSA-QoL motor subscales score at Week 48 of the DB Phase	Continuous	MMRM	Baseline, Weeks 24, 48, Baseline Ext, Weeks 12 Ext, 24 Ext, 36 Ext, 48 Ext
S03	Difference between treatment groups in change from baseline in MSA-QoL non-motor subscales score at Week 48 of the DB Phase	Continuous	MMRM	Baseline, Weeks 24, 48, Baseline Ext, Weeks 12 Ext, 24 Ext, 36 Ext, 48 Ext
S04	Difference between treatment groups in change from baseline in UMSARS Part I and II total score at Week 48 of the DB Phase	Continuous	MMRM	Screening, Baseline, Weeks 4, 12, 24, 36, 48, Baseline Ext, Weeks 12 Ext, 24 Ext, 36 Ext, 48 Ext
S05	Difference between treatment groups in change from baseline in PGI-S score at Week 48 of the DB Phase	Continuous	MMRM	Baseline, Weeks 4, 12, 24, 36, 48
S06	Difference between treatment groups in change from baseline in CGI-S score at Week 48 of the DB Phase	Continuous	MMRM	Baseline, Weeks 4, 12, 24, 36, 48
S07	Difference between treatment groups in change from baseline in UMSARS Part III (orthostatic change in systolic BP, diastolic BP, and heart rate) at Week 48 of the DB Phase	Continuous	MMRM	Screening, Baseline, Weeks 4, 12, 24, 36, 48, Baseline Ext, Weeks 12 Ext, 24 Ext, 36 Ext, 48 Ext
S08	Difference between treatment groups in change from baseline in UMSARS Part IV score at Week 48 of the DB Phase	Continuous	MMRM	Screening, Baseline, Weeks 4, 12, 24, 36, 48, Baseline Ext, Weeks 12 Ext, 24 Ext, 36 Ext, 48 Ext

MMRM = Mixed effects model for repeated measures; ANOVA = Analysis of variance, KM = Kaplan-Meier

6.3.1 Continuous Efficacy Endpoints

Measurements are slotted into analysis visits as described in Section 7.2.

Descriptive Analyses

Summary statistics for parameter values are tabulated at select time points by treatment group during the DB and OLE phases, separately.

Treatment Group Comparison Using MMRM

Treatment groups are compared and assessed using MMRM with the following variables:

- Dependent variable, e.g., modified UMSARS score
- Fixed effects (categorical variables): treatment group, visit, treatment group-by-visit interaction, randomization strata (i.e., disease subtype, diagnostic category, and country). Visit represents on-study analysis visit.
- Covariate (continuous variable): baseline value of dependent variable, baseline neurofilament level
- Random effect: subject

Error degrees of freedom are determined by the Kenward-Roger approximation.

The covariance structure for within subject error will be initially modeled using the unstructured covariance matrix. If the model fails to converge, then a Huynh-Feldt structure will be used, followed by an AR(1) structure.

The following statistics are tabulated from the MMRM at select analysis visits:

- Least-squares mean with standard error (SE) and 95% CI by treatment group
- Difference in least-squares means between treatment groups (Verdiperstat placebo) with df, SE, 95% CI, and p-value.

Treatment Group Comparison Using ANOVA

Treatment groups are compared and assessed using ANOVA with the following variables:

- Dependent variable, e.g., brain volume
- Fixed effects (categorical variables): treatment group, baseline value of the dependent variable, randomization strata (i.e., disease subtype, diagnostic category, and country)

The following statistics are tabulated from the ANOVA results:

- Least-squares mean with standard error (SE) and 95% CI by treatment group
- Difference in least-squares means between treatment groups (Verdiperstat placebo) with df, SE, 95% CI, and p-value.

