and concurrent treatments. Study dropout including dropouts and missed visits due to COVID-19 pandemic (and corresponding discontinuation of assessments) will be handled by a hypothetical strategy to estimate what the outcome would have been at the designated time point if all subjects were continued to be assessed.

d. The mean change from baseline between treatment and placebo on the primary endpoint will be compared at 48 weeks. A significant difference with an error rate of 5% will be required for success.

The summary will be computed using a Mixed Model for Repeated Measures (MMRM) that will include fixed effect factors for treatment group, randomization strata (i.e., disease subtype, diagnostic category, and country), visit, and the treatment group by visit interaction. Baseline modified UMSARS score and the baseline neurofilament level will enter the model as covariates, and subject will be a random effect. Repeated measurements are made on each subject. The covariance structure for within subject error ("R" matrix in SAS proc mixed) will be initially specified as unstructured. If the model fails to converge, then a Huynh-Feldt structure may be used, followed by an AR(1) structure. Error degrees of freedom will be calculated using Kenward-Roger approximation if an unstructured covariance structure fits appropriately; otherwise, a sandwich estimator will be utilized to estimate the covariance structure and degrees of freedom will be calculated using the between-within method.

MMRM-based estimates (i.e., least-squares mean [LSM] with corresponding SD and 95% CI) of values and changes from baseline will be presented by treatment group and week. In addition, the LSM difference in change from baseline between treatment groups (Verdiperstat – placebo) at Week 48 with corresponding SD, 95% CI, and p-value from MMRM will be presented.

Observed values and changes from baseline in the modified UMSARS score will be summarized using descriptive statistics over time by treatment group.

Effect sizes (Cohen's D) of the individual items within the modified UMSARS will also be summarized to assess the strength of the effect of Verdiperstat on each individual item.

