6.3.3.1 S01: Clinical Global Impression of Improvement (CGI-I)

The CGI-I scale is a clinician-rated scale measuring the change in the subject's total improvement from the time of study start. It is scored on a 7- point scale, ranging from 1 (very much improved) to 7 (very much worse), with a score of 4 indicating no change. The CGI-I should be assessed relative to the CGI-S at the Week 0 (Day 1) visit as the reference. The CGI-I will be administered at Weeks 4, 12, 24, 36 and 48 and/or early discontinuation.

The estimand for this endpoint will pursue a hypothetical strategy of estimating the effect of Verdiperstat relative to placebo had all subjects stayed on treatment. Intercurrent events will be handled by only using the on-treatment data.

The number and percentage of subjects in each category will be summarized: very much improved, much improved, minimally improved, no change, minimally worse, much worse, and very much worse. A similar summary table will be generated for CGI-I with combined categories: 1-3 (improved), 4 (no change), 5-7 (worse).

In addition, the CGI-I scores will be transformed into numeric values ranging from 1 to 7 (1 indicating "very much improved" and 7 indicating "very much worse"). Descriptive statistics for the CGI-I score will be presented by visit.

The transformed CGI-I score at Week 48 will be analyzed similar to the MMRM methodology described in Section 6.3.1, but with baseline CGI-S score as the covariate. If found to be statistically significant, similar methods detailed in Section 6.3.2.3 will be employed.

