6.3.3.2 S02: MSA-Quality of Life (MSA-QoL) Motor Subscale

The MSA-QoL is a subject-rated scale that was designed to measure health-related quality of life specifically in subjects with MSA. It assesses activities of daily living and has subscales for motor, non-motor, and emotional/social domains. The MSA-QoL will be administered at Baseline, Weeks 24, 48, Baseline-Extension, Week 12-Extension, Week 24-Extension, Week 36-Extension, Week 48-Extension, and/or early discontinuation.

Change from baseline in the motor subscale score of the MSA-QoL at Week 48 will be analyzed with the MMRM methodology described in Section 6.3.1. If found to be statistically significant, the same methods detailed in Section 6.3.2.3 will be employed.

Descriptive statistics for the MSA-QoL motor subscale score and the change from baseline in the subscale score will be presented by treatment group and visit as described in Section 6.3.1.

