6.3.3.3 S03: MSA-Quality of Life (MSA-QoL) Non-Motor Subscale

The MSA-QoL is described in Section 6.3.3.2.

Change from baseline in the non-motor subscale score of the MSA-QoL at Week 48 will be analyzed with the MMRM methodology described in Section 6.3.1. If found to be statistically significant, the same methods detailed in Section 6.3.2.3 will be employed.

Descriptive statistics for the MSA-QoL non-motor subscale score and the change from baseline in the subscale score will be presented by treatment group and visit as described in Section 6.3.1.

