6.3.3.4 S04: UMSARS Part I and Part II Total Score

As described in Section 6.3.2.1, the UMSARS is a clinician-rated scale comprised of four parts. The Part I (Historical Review) and Part II (Motor Examination) total score will be assessed as a secondary endpoint.

Change from baseline in the UMSARS Part I and Part II total score at Week 48 will be analyzed with the MMRM methodology described in Section 6.3.1. If found to be statistically significant, the same methods detailed in Section 6.3.2.3 will be employed. The UMSARS Part I and Part II total score will exclude item 11 from Part I (sexual function).

Descriptive statistics for the UMSARS Part I and Part II total score and the change from baseline total score will also be presented by treatment group and visit as described in Section 6.3.1.

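### SAP 6.3.1 keeps Kenward-Roger for the four key secondary endpoints even after a covariance fallback, while 6.3.2.1 switches the primary endpoint to sandwich standard errors

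*SAP*

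**What the plan says.** SAP 6.3.1 defines the general MMRM. The covariance starts as unstructured, and "If the model fails to converge, then a Huynh-Feldt structure will be used, followed by an AR(1) structure". On degrees of freedom it says only that "Error degrees of freedom are determined by the Kenward-Roger approximation". It names no sandwich estimator and no alternative method.

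SAP 6.3.2.1 has the same fallback order for the primary endpoint but makes the inference rule conditional: "Error degrees of freedom will be calculated using Kenward-Roger approximation if an unstructured covariance structure fits appropriately". For the case where that condition is not met, the section goes on to name a second rule: "otherwise, a sandwich estimator will be utilized to estimate the covariance structure and degrees of freedom will be calculated using the between-within method".

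Each key secondary endpoint takes its main model from 6.3.1:

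- CGI-I (6.3.3.1): "The transformed CGI-I score at Week 48 will be analyzed similar to the MMRM methodology described in Section 6.3.1", with baseline CGI-S as the covariate.
- MSA-QoL motor (6.3.3.2): "motor subscale score of the MSA-QoL at Week 48 will be analyzed with the MMRM methodology described in Section 6.3.1".
- MSA-QoL non-motor (6.3.3.3): "non-motor subscale score of the MSA-QoL at Week 48 will be analyzed with the MMRM methodology described in Section 6.3.1".
- UMSARS Part I and II total (6.3.3.4): "with the MMRM methodology described in Section 6.3.1".

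The only part of the primary endpoint's analysis plan that these sections invoke is 6.3.2.3, the multiple-imputation sensitivity analysis. They do not invoke the sandwich rule of 6.3.2.1.

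**The concern.** The sponsor wrote a safeguard for one confirmatory endpoint and left it out of the section that governs the other four, without giving a reason. The safeguard has a purpose. Huynh-Feldt and AR(1) restrict the covariance, and if the restriction is wrong the model-based standard error at Week 48 is wrong. Kenward-Roger adjusts for estimating the covariance parameters in a finite sample; it takes the chosen structure as true.

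The direction of the error matters. In a progressive disease, between-subject spread may widen over visits. A structure that pools variance across visits then understates it at the last visit, which is the one tested. If the primary endpoint is significant, these p-values enter the Hochberg procedure of SAP 5.2, with thresholds 0.05/4, 0.05/3, 0.05/2 and 0.05 (0.0125, 0.0167, 0.025, 0.05). An understated standard error therefore feeds directly into a confirmatory claim.

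**Working it through.** **Sample size.** This is not in dispute, but it sets the size of trial used below. SAP 5.1: difference 0.40 × 4.88 = 1.952, SD 4.85. Per group, 2 × (1.960 + 1.282)² × 4.85² / 1.952² ≈ 130, so 260 in total; 260 / 0.80 = 325. The plan's figures reproduce.

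**Covariance assumption.** The documents give one SD (4.85, modified UMSARS, placebo) and none by visit. I assume a random slope plus independent error, with Week 48 variance scaled to 1 and slope share θ:

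V(j,k) = θ (t_j/48)(t_k/48) + (1 − θ) [j = k], at Weeks 4, 12, 24, 36, 48.

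The Week 4 SD relative to Week 48 is √(θ/144 + 1 − θ): 0.895 at θ = 0.2, 0.636 at 0.6 and 0.453 at 0.8.

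**Large-sample error.** In large samples the fitted structure S minimises log|S| + tr(S⁻¹V). With complete data and arm-by-visit means, the Week 48 contrast is the difference in arm means, so

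r = model SE / true SE = √(S₄₈,₄₈ / V₄₈,₄₈), and type I error = 2{1 − Φ(1.96 r)}.

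Example: Huynh-Feldt at θ = 0.6 has r = 0.894; 1.96 × 0.894 = 1.752; two-sided tail 8.0%.

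| Slope share θ | Huynh-Feldt r | Type I error | AR(1) r | Type I error |
|---|---|---|---|---|
| 20% | 0.983 | 5.4% | 0.936 | 6.7% |
| 40% | 0.951 | 6.2% | 0.867 | 8.9% |
| 60% | 0.894 | 8.0% | 0.793 | 12.0% |
| 80% | 0.787 | 12.3% | 0.717 | 16.0% |

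Huynh-Feldt has a variance for each visit, yet it still errs. It forces each covariance to equal the mean of the two variances minus a constant, and the fit gives up Week 48 variance to meet that. If the SD is constant over visits, the rate is 5.0%.

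**Two scheduled visits (MSA-QoL, Weeks 24 and 48).** Huynh-Feldt has two variances and one constant: three parameters, the same as unstructured. It is the same model, and the rate is 5.0%. AR(1) has two parameters and gives 5.9/7.1/8.4/10.1% at θ = 20/40/60/80%.

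**Does Kenward-Roger repair this?** At 325 subjects with 20% dropout, the adjusted SE divided by the model SE is 1.0005 to 1.0006 for Huynh-Feldt (517 to 697 df) and 1.0001 to 1.0002 for AR(1). The shortfall at θ = 0.6 is 1 − 0.894 = 10.6% for Huynh-Feldt, so the answer is no.

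**Does the sandwich rule repair it?** Null simulation, five visits, 162 + 163 subjects, 20% dropout depending on the last observed score in the same way in both arms, 2000 runs per setting (Monte Carlo SE 0.5 points at 5%), θ = 20/40/60/80%:

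| Rule | Huynh-Feldt | AR(1) |
|---|---|---|
| 6.3.1 | 5.4/6.0/9.3/12.1% | 6.5/8.9/14.2/16.6% |
| 6.3.2.1 (sandwich) | 4.8/5.0/6.2/5.4% | 4.8/4.8/6.1/5.5% |

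The unstructured model on the same data gave 4.6/5.0/6.1/5.7%. At θ = 60%, 1431 fresh runs gave 5.2% and 5.3% with the sandwich, against 7.5% and 12.0% with the 6.3.1 rule.

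**Is a fallback likely?** Fitted without a separate subject intercept, the unstructured model converged in 2000 of 2000 runs in all eight settings (four slope shares, at five and at two visits). That was with normal data and not in SAS.

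**The case against.** The strongest reply is that the gap will probably never be used. Harm needs a significant primary endpoint, a fallback for that particular secondary, and variance that grows over visits. The unstructured model is likely to converge with about 325 subjects and 15 covariance parameters at most, and two of the four endpoints are unaffected until the second fallback. The slope shares have no source in the documents, and the largest rates come from the top of the assumed range. All of this stands, and it sets the rating.

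A reader might infer more from the subject random effect listed in both sections. Beside an unstructured or Huynh-Feldt matrix a random intercept is not identified: adding a constant to every entry of either matrix gives another matrix of the same type. One could then argue that both fits count as failures, so that the five-visit endpoints must end at AR(1). The documents do not support this. They do not say that a redundant term counts as non-convergence, and software may report convergence. Since 6.3.2.1 places the covariance in the R matrix of SAS proc mixed, the subject entry may only identify the repeated-measures unit.

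A reader might also cite Protocol 9.4.3, which gives the change-from-baseline secondaries the primary's strategy. That may refer only to the estimand, and Protocol 9.4.2 contains no sandwich or degrees-of-freedom rule to inherit.

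Finally, the simulated rates near 5% for the sandwich hold for equal dropout mechanisms in the two arms. In 400 null trials per setting at θ = 80% (Monte Carlo SE 1.3 to 1.8 points), outcome-dependent dropout in one arm only gave 7.8% (Huynh-Feldt) and 9.2% (AR(1)) with the sandwich, against 15.2% and 23.2% under 6.3.1. With opposite directions in the two arms it was 8.8% and 15.5%, against 17.8% and 33.2%. The sandwich corrects the standard error, not a biased estimate. It is still the better rule in each setting.

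**Conclusion.** The inconsistency is plain in the text and holds for all four key secondary endpoints. Its effect is conditional and the point is minor. If a fallback is used and slopes make up 20 to 60% of Week 48 variance, type I error per nominal 5% test is 5.4 to 8.0% with Huynh-Feldt and 6.7 to 12.0% with AR(1) for CGI-I and the UMSARS Part I and II total. It is higher at larger shares and 5.0% with constant SD. For the MSA-QoL subscales only the AR(1) step matters. These are rates per test, not familywise rates, and they rest on an assumed covariance.

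It would be wrong to conclude that the key secondary analyses are anti-conservative as planned: if the unstructured model converges, nothing changes. Nor is the primary endpoint the target, since 6.3.2.1 gives it the sandwich rule.

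**What to change.** In SAP 6.3.1, replace the degrees-of-freedom sentence with the rule of 6.3.2.1: *Kenward-Roger is used if the unstructured model converges; otherwise sandwich standard errors with between-within degrees of freedom are used.* Use the same trigger, failure to converge, in both sections. At present 6.3.2.1 ties the fallback to convergence but the inference rule to adequate fit.

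As a secondary clarification, state that no separate random subject intercept is fitted beside an unstructured or Huynh-Feldt R matrix, where it is not identified.

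The cost is SAP wording only: no new data, no change in sample size, and no effect on results if the unstructured model converges. If a fallback is used, standard errors are slightly less efficient and the critical value is about 1.968 (about 300 df), against 1.963 to 1.965 under Kenward-Roger at 517 to 697 df. The change does not remove bias in the estimate from a wrong covariance when dropout mechanisms differ between arms.

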6.1.4 Adjustments for Covariates and Stratification

The randomization was stratified by disease subtype (MSA-P vs. MSA-C), diagnostic category (possible MSA vs. probable MSA), and country. Hence, treatment group comparisons of continuous efficacy endpoints will be adjusted by disease subtype, diagnostic category, and country. If there are sparse data within a stratum, then stratum may be combined.

The analysis of the primary endpoint and other continuous efficacy endpoints will also be adjusted by the baseline value of the endpoint as a covariate in statistical models.

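### The SAP's ANOVA block types the baseline value as categorical, against the SAP's own covariate rule; coded literally for a finely measured endpoint, it would leave few or no residual degrees of freedom

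*SAP*

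**What the plan says.** SAP 6.3.1 (Continuous Efficacy Endpoints) sets out two models.

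- **MMRM.** Categorical fixed effects have one line and continuous terms another: "Covariate (continuous variable): baseline value of dependent variable, baseline neurofilament level".
- **ANOVA.** The example response is "Dependent variable, e.g., brain volume". There is a single line of model terms, "Fixed effects (categorical variables): treatment group, baseline value of the dependent variable, randomization strata", and no line for continuous covariates. The output promised is least-squares means and their difference, with degrees of freedom, standard error, 95% confidence interval and p-value.

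Elsewhere the SAP treats baseline differently. Section 6.1.4 says that continuous efficacy endpoints are "adjusted by the baseline value of the endpoint as a covariate in statistical models", and handles the randomization strata in a separate sentence. Section 6.3.2.1 says of the primary model: "Baseline modified UMSARS score and the baseline neurofilament level will enter the model as covariates". The last-on-treatment-visit analysis in 6.3.2.2 and the post-imputation analysis in 6.3.2.3 are both called ANCOVA and both have baseline modified UMSARS as a covariate.

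**The concern.** A categorical effect gets one parameter per distinct value. Brain volume is a measurement, so most subjects may have a baseline that nobody else shares. Under class coding such a subject is the only member of a level, is fitted exactly, and contributes nothing to either the treatment contrast or the residual variance. If nearly all subjects are in that position, the outputs that 6.3.1 promises cannot be produced or are very imprecise.

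The MMRM block a few lines above separates the two types of term, so the ANOVA line reads as an explicit typing of baseline, and it is the wrong type. A programmer would then have to choose between two SAP statements, or depart from one of them without a record. Pre-specification is meant to prevent that.

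**Working it through.** **Sample sizes used.** The documents give no degrees of freedom for the ANOVA, so the check needs only N. SAP 5.1 supplies it, and its figure reproduces. The effect is 0.40 × 4.88 = 1.952 points with SD 4.85. Then n per arm = 2 × (1.960 + 1.2816)² × 4.85² / 1.952² = 2 × 10.507 × 23.5225 / 3.8103 = 129.7, rounded up to 130. Power at 130 per arm is 0.901 (normal) or 0.898 (noncentral t). Allowing for 20% dropout, 260 / 0.80 = 325. Both 260 and 325 are used below.

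**Degrees of freedom by count.** Let C be the number of countries and k the number of distinct baseline values.

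- Baseline continuous: intercept 1, treatment 1, subtype 1, diagnostic category 1, country C − 1, baseline 1. Residual df = N − (C + 4). For C = 4 to 12 this is 317 to 309 at N = 325, and 252 to 244 at N = 260.
- Baseline as a class: the single baseline term becomes k − 1. Residual df = N − (C + 2 + k) when the columns are independent. Example: N = 325, C = 4, k = 210 gives 325 − 216 = 109.
- All values distinct (k = N): the baseline columns with the intercept already have rank N. Residual df = 0, and the treatment column adds no rank, so treatment is not estimable.

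**Intermediate cases.** Design matrices were simulated, one draw per setting, with 1:1 allocation, both two-level strata, and 4, 8 or 12 countries. Country count, a volume SD of 100 units and the recording precision are assumptions; the documents state none of them. The SE ratio compares class coding with the continuous-covariate model on the same draw. Ranges run over the country counts.

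| Baseline | Residual df, N = 325 | SE ratio | Residual df, N = 260 | SE ratio |
|---|---|---|---|---|
| All distinct | 0 | not estimable | 0 | not estimable |
| Volume to 0.1 unit | 1 to 10 | see below | 0 | see below |
| Volume to 1 unit | 93 to 109 | 1.77 to 1.81 | 59 to 73 | 1.74 to 2.04 |
| Volume to 5 units | 223 to 232 | 1.16 to 1.19 | 167 to 172 | 1.21 to 1.26 |
| Volume to 10 units | 264 to 268 | 1.06 to 1.11 | 200 to 206 | 1.10 to 1.13 |
| Score from 0 to 27 | 290 to 300 | 1.03 to 1.04 | 225 to 234 | 1.02 to 1.04 |
| 7-point scale | 304 to 312 | 1.00 to 1.01 | 239 to 248 | 1.00 to 1.01 |

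At 0.1-unit recording (251 to 315 distinct values) treatment was not estimable in three of the six settings. In two others, at N = 325, the SE was 0.58 and 1.13 residual SDs, against 0.11 for the covariate model. In the sixth (N = 260, 8 countries) the contrast existed, with a multiplier of 1.41, but 0 residual df leaves no variance estimate and hence no usable SE.

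**Does another rule rescue the literal model?** Section 6.1.4 has a sparse-data provision, "If there are sparse data within a stratum, then stratum may be combined". It covers strata and does not allow baseline levels to be merged.

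**Which endpoints use the ANOVA?** In Table 4 of the SAP, P01 and S01 to S08 are all assigned MMRM. The table's footnote defines ANOVA although no visible row uses it, which fits redacted rows. Protocol 9.4.3 does plan an analysis of variance for CGI-I with baseline CGI-S among the factors, but SAP 6.3.3.1 specifies an MMRM with baseline CGI-S as the covariate. Even under the protocol's wording CGI-S has 7 levels, which is the last row of the table.

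**The case against.** The strongest reply is that 6.1.4 already governs. The ANOVA block sits under a heading on continuous efficacy endpoints, 6.1.4 says such endpoints are adjusted for baseline as a covariate, and the other single-timepoint models follow that rule. On this view the ANOVA line is a labelling slip. A saturated fit would also show itself through missing standard errors, so it would be noticed at programming and would not silently bias a result.

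Most of this stands. It is good evidence of intent and limits the practical harm. It does not make the text right: 6.3.1 is the detailed specification, and it types the term explicitly. Nor is detection assured. With coarser recording the model fits, prints a p-value, and merely loses precision.

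A reader might go further and infer that every endpoint under this ANOVA would be inestimable, or that the trial's main tests are affected. The documents support neither. Inestimability needs both literal class coding and nearly all-distinct baselines; the documents give no recording precision for brain volume, and a short ordinal baseline loses almost nothing. The primary and secondary comparisons do not use this model.

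**Conclusion.** The ANOVA line in SAP 6.3.1 is wrong as written and inconsistent with the rest of the SAP. For a finely measured continuous endpoint, such as the one the SAP names, literal coding leaves 0 residual degrees of freedom and no treatment estimate if all baselines are distinct. If they are nearly all distinct, it leaves 0 to 10. With coarser recording the cost is precision only: standard errors about 1.7 to 2.0 times those of the covariate model at 1-unit recording, 6% to 26% larger at 5 to 10 units, and at most about 1% larger for a 7-point scale. The two exact results (0 df, and N − (C + 4) for the covariate model) follow from counting. The intermediate figures rest on the assumed SD, precision and country counts.

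The reach is narrow. Primary and secondary inference, the Hochberg family in SAP 5.2 and the sample size are untouched. The number and scale of the endpoints that do use this ANOVA cannot be checked from the public text. This is a minor correction, worth making before programming.

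**What to change.** In the ANOVA block of SAP 6.3.1, take the baseline value of the dependent variable out of the categorical list and put it on its own continuous-covariate line, as the MMRM block does. Treatment group and the randomization strata stay categorical. Rename the model ANCOVA, to match 6.3.2.2 and 6.3.2.3, and carry the name into Table 4 and its footnote.

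The cost is one moved term and a label. Baseline then uses 1 degree of freedom, 244 to 317 remain under the country counts assumed here, and no primary or secondary analysis changes. There is no statistical downside.
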